### **7.2.1 Group 1: Baseline/Randomization/Visit 2 (Day -2 to -1)**

After a subject has successfully completed the screening procedures he or she will return to the investigative site to complete his or her baseline procedures. The subject may be admitted to the study center the day before (Day -2) the MWT to complete selected assessments provided that it falls within the visit window (listed in [Appendix 2](#)). Individual assessments should be performed on the same study day at approximately the same time of day across study visits.

On admission to the study center in the morning (at approximately 8:00 AM on Day -1), complete the following (as listed in [Appendix 2](#)):

- Document the date(s) that excluded medications were discontinued and any other changes to concomitant medications since screening. Record all AEs that occur after the ICF was signed. Verify and ensure PD and sleep medications were taken and continue to be taken at the same dose and regimen. For subjects currently receiving treatment for OSA, review OSA therapy device usage to ensure adequate compliance.
- Administer the ESS Questionnaire.

- Administer the MDS-UPDRS (Parts III and IV). When feasible, the MDS-UPDRS (Parts III and IV) is to be performed on the same study day and approximate same time for each subsequent visit while the subject is in the “on” state.
- Complete the CGIs.
- Perform physical examination.
  - Obtain weight in ordinary indoor clothes (without shoes).
- Obtain vital signs (systolic and diastolic blood pressure [seated and standing], pulse rate [seated and standing], respiratory rate, and body temperature), including at least 2 sets of blood pressure and pulse rate measurements in the seated position after the subject has been resting and seated for at least 5 minutes. Next, standing blood pressure and pulse rate should be taken at 1 and 3 minutes after the subject has been standing.
- 12-lead ECG after the subject has been resting supine for at least 5 minutes.
- If the Baseline visit occurs outside of the screening window (i.e., >29 days after the Screening Visit), obtain safety laboratory blood samples for serum chemistry and hematology tests and a urine sample for urinalysis. Record if the samples were collected with the subject fasted or nonfasted.
- Obtain a urine sample for a pregnancy test for all females of childbearing potential (see [Table 1](#) for definitions of childbearing potential).
- Complete breath alcohol screen test.

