- Approximately 6 hours after dosing, obtain a 12-lead ECG after the subject has been resting supine for at least 5 minutes.

- [Optional Assessment] If feasible, approximately 7 hours after dosing, initiate the fourth trial of the MWT.
- Document any AEs that occurred since the last visit.
- The safety findings will be reviewed by the investigator, who will decide whether or not to proceed to the next dose.
- Dispense study drug and instruct subject on the daily dose administration to begin on the following morning.
- Complete drug accountability.
- Schedule the next return clinic visit.

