## Appendix 2      Group 1: Example Time Schedule for Procedures During the Baseline Visit

Note: This is a sample schedule and time of arrival at the study center can be shifted as needed based on the patient's typical sleep periods and individual site logistics. Individual assessments should be performed at approximately the same time of day across study visits.

Baseline Visit	
Approximate Time	Procedure/Activity
8:00	
Subject arrives at study centera
 
Assess any updates to medical history and changes in concomitant medications. Record all AEs that occur after the ICF was signed. Verify and ensure PD and sleep medications were taken and continue to be taken appropriately. For subjects currently receiving treatment for OSA, review OSA therapy device usage to ensure adequate compliance.a
 
Administer the ESS Questionnairea
 
Administer the MDS-UPDRS (Parts III and IV)a,b
 
Complete the CGIsa
 
Physical examination and weighta
 
Body temperature, respiratory rate, and at least 2 sets of blood pressure and pulse in seated position; then blood pressure and pulse at 1 and 3 minutes after standing
 
ECGa
 
Safety laboratory blood samplesa,c
 
Urine sample for urinalysisa
 
Urine pregnancy test (for all females of childbearing potential)a
 
Alcohol breath screening testa

9:15	Light breakfast
9:50	At least 2 sets of blood pressure and pulse in seated position; then blood pressure and pulse at 1 and 3 minutes after standing
10:00d	
Ask the subject the following question: "How long did you sleep last night?"
 
Start first MWT triald

11:00	At least 2 sets of blood pressure and pulse in seated position; then blood pressure and pulse at 1 and 3 minutes after standing
11:15	Complete the FSS, Apathy Scale, SCOPA-cog, and C-SSRS Questionnaires a
12:00	Start second MWT trial
	Light lunch served immediately after the end of the second trial
13:00	At least 2 sets of blood pressure and pulse in seated position; then blood pressure and pulse at 1 and 3 minutes after standing
14:00	Start third MWT trial
16:00	Start fourth MWT trial (optional)

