CGIs = Clinical Global Impression of Severity; C-SSRS = Columbia-Suicide Severity Rating Scale; ECG = electrocardiogram; ESS = Epworth Sleepiness Scale; I/E = inclusion/exclusion; MDS-UPDRS = Movement Disorders Society-Unified Parkinson's Disease Rating Scale; MWT = maintenance of wakefulness test; FSS = Fatigue Severity Scale; SCOPA cog = Scales for Outcomes in Parkinson's disease-cognition

a These assessments can be performed the day before (Day -2) the MWT, provided it falls within the visit window.

b When feasible, the MDS-UPDRS (Parts III and IV) is to be performed on the same study day and approximate same time for each subsequent visit while the subject is in the "on" state.

c If the Baseline visit occurs outside of the screening window (i.e., >29 days after the Screening visit), obtain blood samples for serum chemistry and hematology and a urine sample for urinalysis.

d The first MWT trial should be started approximately 1.5 to 3 hours after the time of the subject arising that morning.

## Appendix 3      Group 1: Example Time Schedule for Procedures at Visits 3, 4, 5, or 6

Note: This is a sample schedule and time of arrival at the study center can be shifted as needed based on the patient's typical sleep periods and individual site logistics. Individual assessments should be performed at approximately the same time of day across study visits.

Visits 3, 4, 5, and 6		
Time Relative to Dosing	Approximate Time	Procedure/Activity

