~ -1 h	8:00	Subject arrives at study center a Record all concomitant medications taken since last visit. Record all AEs. Verify and ensure PD medications, sleep medications allowed by the protocol, and study drug (as specified in Section 5.3 of the protocol) were taken and continue to be taken appropriately. For subjects currently receiving treatment for OSA, review OSA therapy device usage to ensure adequate compliance. a Administer the ESS Questionnaire a Administer the MDS-UPDRS (Parts III and IV) a,b Complete the CGIC a Physical examination and weight a Body temperature, respiratory rate, and at least 2 sets of blood pressure and pulse in seated position; then blood pressure and pulse at 1 and 3 minutes after standing ECG Safety laboratory blood samples a Urine sample for urinalysis a Urine pregnancy test (for all females of childbearing potential) a Alcohol breath screening test a
0 h	9:00	Dosing
~0.25 h	9:15	Light breakfast
~1 h	9:50	At least 2 sets of blood pressure and pulse in seated position; then blood pressure and pulse at 1 and 3 minutes after standing
~1 h	10:00c	Ask the subject the following question: "How long did you sleep last night?" Start first MWT trialc
~2 h	11:00	At least 2 sets of blood pressure and pulse in seated position; then blood pressure and pulse at 1 and 3 minutes after standing
~2.25 h	11:15	Complete the PGIC, FSS, Apathy Scale, SCOPA-cog, and C-SSRS Questionnaires a
~3 h	12:00	Start second MWT trial Light lunch served immediately after the end of the second trial
~4 h	13:00	At least 2 sets of blood pressure and pulse in seated position; then blood pressure and pulse at 1 and 3 minutes after standing
~5 h	14:00	Start third MWT trial
~6 h	15:00	At least 2 sets of blood pressure and pulse rate measurements in seated position; then standing blood pressure and pulse rate measurements at 1 and 3 minutes after standing ECG
~7 h	16:00	Start fourth MWT trial (optional)

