## Appendix 5      Group 2: Example Time Schedule for Procedures During the Baseline Visit

Note: This is a sample schedule and time of arrival at the study center can be shifted as needed. Individual assessments should be performed at approximately the same time of day across study visits.

Baseline Visit	
Approximate Time	Procedure/Activity
8:00	
Subject arrives at study center
 
Assess any updates to medical history and changes in concomitant medications. Record all AEs that occur after the ICF was signed. Verify and ensure PD and sleep medications were taken and continue to be taken appropriately. For subjects currently receiving treatment for OSA, review OSA therapy device usage to ensure adequate compliance.
 
Administer the ESS Questionnaire
 
Administer the C-SSRS Questionnaire
 
Body temperature, respiratory rate, and at least 2 sets of blood pressure and pulse in seated position; then blood pressure and pulse at 1 and 3 minutes after standing
 
Physical examination and weight
 
Safety laboratory blood samplesa
 
Urine sample for urinalysisa
 
Urine pregnancy test (for all females of childbearing potential)
 
Alcohol breath screening test

9:15	Light breakfast
10:00	At least 2 sets of blood pressure and pulse in seated position; then blood pressure and pulse at 1 and 3 minutes after standing
10:30	Complete the FSS, Apathy Scale, and SCOPA-cog Questionnaires
11:00	
At least 2 sets of blood pressure and pulse in seated position; then blood pressure and pulse at 1 and 3 minutes after standing
 
ECG
 
Complete the CGIs
 
Administer the MDS-UPDRS (Parts III and IV)b

AE = adverse event; CGIs = Clinical Global Impression of Severity; C-SSRS = Columbia-Suicide Severity Rating Scale; ECG = electrocardiogram; ESS = Epworth Sleepiness Scale; ICF = informed consent form; I/E = inclusion/exclusion; MDS-UPDRS = Movement Disorders Society-Unified Parkinson's Disease Rating Scale; FSS = Fatigue Severity Scale; PD = Parkinson's disease; SCOPA cog = Scales for Outcomes in Parkinson's disease-cognition

a If the Baseline visit occurs outside of the screening window (i.e., >29 days after the Screening visit), obtain blood samples for serum chemistry and hematology and a urine sample for urinalysis.

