### 17.3. ECG EVALUATIONS

The following ECG parameters will be reported for this study based on core laboratory values:

- HR (beats per minute [bpm])
- RR interval (msec)
- PR interval (msec)
- QRS interval (msec)
- QT interval (msec)
- QT Fridericia's correction (QTcF) interval (msec) [derived]
- QT Bazett's correction (QTcB) interval (msec) [derived]
- Overall evaluation of ECG:
  - Normal
  - Abnormal, not clinically significant
  - Abnormal, clinically significant

The following summaries will be provided based on SAF for ECG data:

- Observed values and change from Baseline to end of period post-dose timepoint (for quantitative measurements)
- Observed values and change from end of period pre-dose timepoint to end of period post-dose timepoint (for quantitative measurements)
- Incidence of markedly abnormal criteria from Baseline to end of period post-dose timepoint (refer to Section 17.3.2 for details) by gender
- Incidence of markedly abnormal criteria from end of period pre-dose timepoint to end of period post-dose timepoint (refer to Section 17.3.2 for details) by gender
- Shift from Baseline to end of period post-dose timepoint in ECG overall evaluation by gender
- Shift from end of period pre-dose timepoint to end of period post-dose timepoint in ECG overall evaluation by gender

- Incidence of subjects for which their ECG overall evaluation improved, remained unchanged or worsened from Baseline to end of period post-dose timepoint by gender
- Incidence of subjects for which their ECG overall evaluation improved, remained unchanged or worsened from the end of period pre-dose timepoint to the end of period post-dose timepoint by gender
- Incidence of subjects with at least one ECG diagnosis by diagnosis category (i.e., rate/rhythm, conduction abnormalities, changes in ST segment, axis, chamber enlargement, myocardial infarction, and miscellaneous) and diagnosis by visit, timepoint, and gender

The following listings will be provided:

- Listing of subjects with any observed QT, QTcB, or QTcF values >450 msec and/or change from Baseline in QT, QTcB, or QTcF >30 msec
- Listing of subjects with any abnormal ECG overall evaluation

The following figures will be provided:

- Line plot of mean observed values across visit by sequence and treatment group;

[figure not shown]

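### Group 1's change-from-Baseline ECG results compare an ECG at about 08:00 with one at about 15:00, so within-treatment changes and threshold counts mix time of day with drug effect

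*Protocol*

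**What the plan says.** **Timing rule.** The note at the head of protocol Appendix 2 states: "Individual assessments should be performed at approximately the same time of day across study visits".

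**Group 1, Baseline.** Protocol Section 7.2.1 opens its procedure list with "On admission to the study center in the morning (at approximately 8:00 AM on Day -1), complete the following", and that arrival list contains the one scheduled ECG: "12-lead ECG after the subject has been resting supine for at least 5 minutes". Appendix 2 shows it in the 08:00 block, ahead of the 09:15 breakfast. Footnote a to that ECG adds: "These assessments can be performed the day before (Day -2) the MWT, provided it falls within the visit window".

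**Group 1, Visits 3 to 6.** There is a pre-dose ECG at about 08:00 and then, in Section 7.2.2, "Approximately 6 hours after dosing, obtain a 12-lead ECG after the subject has been resting supine for at least 5 minutes". Appendix 3 places dosing at 09:00 and the second ECG at 15:00, after lunch and the third MWT trial.

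**Group 2.** Appendix 5 puts the Baseline ECG in the 11:00 row ("ECG Complete the CGIs"). Section 7.3.2 and Appendix 6 put the post-dose ECG about 2 hours after dosing, also 11:00.

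**Analysis.** SAP Section 17.3 lists "Observed values and change from Baseline to end of period post-dose timepoint (for quantitative measurements". The markedly abnormal incidences, the shift tables and the improved/worsened tables run over the same interval. SAP Section 6.2 defines Baseline as the last non-missing value before first dose, with no reference to clock time. SAP Section 17.4.2 pairs Baseline and visit timepoints by clock time for seated blood pressure and pulse; Section 17.3 has nothing comparable for ECG. Nor does it separate Group 1 from Group 2.

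**The concern.** A change from Baseline describes a treatment effect only if the two readings differ in little else. In Group 1 the two ECGs also differ in time of day, in meals, and in hours spent sitting through wakefulness trials. Heart rate may change with all of these, and the >30 and >60 msec criteria in SAP Section 17.3.2 apply to uncorrected QT as well as QTcF.

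Safety is the primary objective and is descriptive only, so these tables are the ECG result. The plan has no placebo-corrected ECG estimate. Readers are likely to take the within-dose mean changes and the counts above 30 and 60 msec at face value.

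**Working it through.** **1. Clock times (Appendices 2, 3, 5 and 6).**

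| | Baseline ECG | Post-dose ECG | Gap |
|---|---|---|---|
| Group 1 | 08:00 | 09:00 + 6 h = 15:00 | 15:00 − 08:00 = 7 h |
| Group 2 | 11:00 | 09:00 + 2 h = 11:00 | 0 h |

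The 15:00 figure reproduces the clock time printed in Appendix 3. If the Group 1 Baseline ECG falls anywhere between 08:00 and 09:15, the gap is 5.75 to 7 h.

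**2. Does the SAP's other ECG contrast remove the gap?** Section 17.3 also compares the same-day pre-dose and post-dose ECGs. In Group 1 that spans 15:00 − 08:00 = 7 h, and in Group 2 it spans 11:00 − 08:00 = 3 h. It does not. The only clock-matched Group 1 pair, Baseline with pre-dose (both about 08:00), is not among the listed contrasts.

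**3. Was matching available in principle?** For blood pressure and pulse, the Baseline times 0, 2, 3 and 5 h (08:00, 10:00, 11:00, 13:00) are paired with pre-dose, 1, 2 and 4 h (08:00, 10:00, 11:00, 13:00). The same cannot be done afterwards for Group 1 ECGs, because no Baseline ECG is scheduled near 15:00.

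**4. Pooled tables.** With a share w of subjects in Group 1, the average gap is 7w hours. The documents give no w. For 0, 25, 50, 75 and 100% the average is 0, 1.75, 3.5, 5.25 and 7 h.

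**5. Effect on a threshold count (illustration only).** The documents give neither the shift nor the SD. Assume a shift d between −10 and +10 msec and a single-ECG change that is normal with SD 15 msec. Then P(change > 30) = 1 − Φ((30 − d)/15). With no drug effect:

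| d (msec) | −10 | −5 | 0 | +5 | +10 |
|---|---|---|---|---|---|
| Rate above 30 msec | 0.4% | 1.0% | 2.3% | 4.8% | 9.1% |

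The assumed SD matters as much as the shift. With SD 12 the rate is 0.6% at zero shift and 4.8% at +10; with SD 18 it is 4.8% and 13.3%.

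**6. What cancels against placebo.** Let the drug effect be δ and the shift d. The mean change is δ + d on drug and d on placebo, so the difference is δ whatever d is. Counts do not behave this way. With an assumed δ of +10 msec and SD 15:

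| d (msec) | Drug | Placebo | Excess |
|---|---|---|---|
| −10 | 2.3% | 0.4% | 1.9 points |
| 0 | 9.1% | 2.3% | 6.8 points |
| +10 | 25.2% | 9.1% | 16.1 points |

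**The case against.** The strongest reply is that the comparison that matters is with placebo, and placebo visits follow the same 08:00 and 15:00 schedule. SAP Section 17 shows every safety table by treatment, with placebo also split by sequence. A reader can therefore see a common shift in the placebo column. A +10 msec drug effect offset by a −10 msec shift would show 0 on drug, but −10 on placebo beside it, so the effect would not be hidden. This stands for mean changes. It stands only in part for threshold counts, as step 6 shows.

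The sizes in msec are wholly assumed, and even the direction of the shift is unknown. Protocol Sections 1.3.3 and 1.3.6 report no effect on ECG intervals in the 12-week narcolepsy study and no clinically significant ECG effects overall, which lowers the stakes. Both points stand.

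Two stronger readings are tempting, and the documents do not support them.

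- A reader might infer that Group 1 violates the same-time-of-day instruction. It does not. The morning ECG recurs at about 08:00 at Baseline and at Visits 3 to 6, and the afternoon ECG recurs at about 15:00 at Visits 3 to 6. The afternoon ECG simply has no Baseline counterpart.
- A reader might take footnote a as permission for a Day -2 ECG at any hour. It names no hour, but Section 7.2.1 gives the Day -2 option and asks for a similar time of day in the same paragraph. A narrower point remains: that paragraph also asks for the same study day across visits, and the visit ECG in Appendix 3 carries no day-before footnote.

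**Conclusion.** The point holds as a limitation on interpretation. Group 1's within-treatment ECG changes, counts above 30 and 60 msec, new values above 450 msec and shift tables rest on readings roughly 6 to 7 hours apart, and nothing planned removes that component. Mean dose-minus-placebo differences largely survive, apart from any difference in Group 1/Group 2 mix between treatments. A reader might go further and call the tables meaningless; with a placebo column on the same schedule, that is not justified.

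The hours come from approximate sample schedules that sites may shift. The size in msec cannot be derived from the documents. The ECG schedule for subjects enrolled before Amendment 2 is not in these documents, so the point cannot be assumed to apply to them. This is a desirable improvement, not one on which the safety conclusions depend.

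**What to change.** **SAP Section 17.3.** For Sequences A and B, add the within-subject difference between each dose-visit post-dose ECG and the placebo-visit post-dose ECG at the same clock time, with counts above 30 and 60 msec on that difference. Present it by Group, because post-dose means about 6 h in Group 1 and about 2 h in Group 2. Show it beside the change from Baseline, not in place of it: Sequence C has no dose visit, and a Sequence B subject who leaves before Period 4 has no placebo visit. The data are already scheduled, and the cost is one descriptive table.

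**Protocol Section 7.2.1 and Appendix 2, for Group 1 subjects not yet enrolled.** Move the Baseline ECG to about 15:00 on Day -1 and remove footnote a from it. The slot lies between the third MWT trial (14:00) and the optional fourth (16:00). Randomization and dispensing are listed after the trials, so the subject is still on site. No ECG is added, and the ECG exclusion criterion is judged at Screening. Two costs follow: the 08:00 Baseline match to the pre-dose ECG is lost, though no listed SAP contrast uses it, and a mid-trial change leaves two Baseline ECG times within Group 1. The table footnotes should say so.

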## Appendix 4      Group 2: Schedule of Events

	Screen	BL	Treatment Phase				ET	Safety Follow-up
Visit	1	2	3	4	5	6		7
Day End of Week	Days -31 to -3	Day -1	Day 7 (±1) Week 1	Day 14 (±1) Week 2	Day 21 (±1) Week 3	Day 28 (±1) Week 4		Day 35 (±1) Week 5
Clinic visit	X	X	X	X	X	X	X	X
Informed Consent	X							
Demographics	X							
ESS	X	X	X	X	X	X		X
Berlin Sleep Apnea Questionnaire		X						
UK PDS Brain Bank Criteria	X							
MDS-UPDRS Parts III and IV a (on-state)			X	X	X	X		
CGIs		X						
CGIc			X	X	X	X		
Medical History	X							
Prior and Concomitant Medications and Therapies	X	X b	X b	X b	X b	X b	X	X
Physical Examination	X	X	X	X	X	X	X	X
Height	X							
Weight	X	X	X	X	X	X	X	X
Calculate BMI	X							
Vital Signs c	X	X	X	X	X	X	X	X
QUIP-RS	X							
BDI-2	X							
C-SSRS	X	X	X	X	X	X	X	X
12-Lead ECG	X	X	X	X	X	X	X	X
Safety Laboratory Tests d	X	X e	X	X	X	X	X	X
Urinalysis	X	X e	X	X	X	X	X	X
Serum Pregnancy Test f	X							
Urine Pregnancy Test f		X	X	X	X	X	X	X
Urine Drug Screen	X							
Alcohol Breath Test	X	X	X	X	X	X	X	X
Study Drug Administration			X	X	X	X		
Light Breakfast and/or Lunch g	X	X	X	X	X	X	X	
PGIc			X	X	X	X		
FSS		X	X	X	X	X		
Apathy Scale		X	X	X	X	X		
SCOPA-cog	X	X	X	X	X	X		
Adverse Event Assessment	X	X	X	X	X	X	X	X
Review I/E Criteria	X	X						
Randomization		X						
Dispense Study Drug		X	X	X	X			
Drug Accountability			X	X	X	X	X	

BDI-2 = Beck Depression Inventory-2; BL = baseline; BMI = body mass index; CGIc = Clinical Global Impression of Change; CGIs = Clinical Global Impression of Severity; C-SSRS = Columbia-Suicide Severity Rating Scale;

ECG = electrocardiogram; ESS = Epworth Sleepiness Scale; ET = Early Termination; FSS = Fatigue Severity Scale; I/E = inclusion/exclusion; MDS-UPDRS = Movement Disorders Society-Unified Parkinson's Disease Rating Scale; PDS = Parkinson's Disease Society; PGIc = Patient Global Impression of Change; QUIP-RS = Questionnaire for Impulsive-Compulsive Disorders in Parkinson's disease Rating Scale; SCOPA-cog = Scales for Outcomes in Parkinson's disease-cognition; UK = United Kingdom

- a The Hoehn and Yahr stage is assessed in Part III of the MDS-UPDRS.
- b Review concomitant medications to verify PD medications, sleep medications allowed by the protocol, and when applicable, study drug (as specified in [Section 5.3](#)) were taken appropriately. For subjects currently receiving treatment for OSA, review OSA therapy device usage to ensure adequate compliance.
- c At the Baseline visit, vital signs (body temperature, respiratory rate, blood pressure [seated and standing], and pulse [seated and standing]) will be taken as soon as possible upon arrival at the study center. Additional blood pressure [seated and standing], and pulse [seated and standing] measurements will be taken at approximately 2 and 3 hours after the first set of vital signs (see [Section 7.3](#) for details). On Treatment Visits 3, 4, 5, and 6, vital signs (body temperature, respiratory rate, blood pressure [seated and standing], and pulse [seated and standing]) will be taken approximately 1 hour prior to dosing at the clinic. Additional blood pressure [seated and standing], and pulse [seated and standing] measurements will be taken at approximately 1 and 2 hours after dosing (see [Section 7.3.2](#) for details). On Safety Follow-up, vital signs (body temperature, respiratory rate, blood pressure [seated and standing], and pulse [seated and standing]) will also be taken.
- d Additional safety laboratory samples may be obtained at the investigator's discretion.
- e If the Baseline visit occurs outside of the screening window (i.e., >29 days after the Screening visit) obtain blood samples for serum chemistry, hematology and a urine sample for urinalysis.
- f Subjects who are not of childbearing potential (i.e., postmenopausal, surgically sterile, or who have medically documented ovarian failure will not need to undergo pregnancy testing).
- g At the Screening and ET visits, subjects may be provided a light breakfast as described in [Sections 7.1](#) and [7.5](#), respectively. At Baseline and at Visits 3, 4, 5, and 6, subjects may be provided a light breakfast as described in [Section 7.3.2](#).

